9. STATISTICAL CONSIDERATIONS

9.1. Statistical Design

This is a Phase 1/2, open-label, 2-part, multi-center study of BDTX-189. Part A is designed primarily to determine the RP2D and dosing schedule, and to characterize the safety, tolerability, PK profile, preliminary antitumor activity, and effect of food on BDTX-189 PK.

Part B is an open label, multi-center, Phase 2 basket study to investigate the antitumor activity of BDTX-189 as a single oral agent in patients with a tumor harboring an eligible allosteric *ErbB* mutation.

Each part will be analyzed and summarized separately. Descriptive statistics will be used to summarize the study data overall and by dose level cohort for Part A unless otherwise specified.

Additional details on statistical design and evaluation of specific endpoint variables are provided in the Statistical Analysis Plan (SAP).

9.2. Estimands

The primary estimand for Part A is the rate at which DLTs occur after treatment with BDTX-189 when administered either QD or BID. It is further described by the following attributes:

- Population: Patients with advanced solid malignancies as reflected by the inclusion/exclusion criteria outlined in Sections 3.1 and 3.2.
- Variable: DLTs, as defined in Section 4.3.2, occurring during the first 21 days of treatment (i.e., Cycle 1).
- Population-level summary: DLT rate, which is defined as the proportion of patients who experience a DLT during Cycle 1. Separate summaries will be estimated for each evaluated dose level of BDTX-189.
- Intercurrent events: Estimation will be based on the hypothetical situation that all patients either receive at least 75% of their planned doses of BDTX-189 during their first 21 days of treatment or experience a DLT during their first 21 days of treatment (i.e. are considered DLT-evaluable). Patients who are DLT-evaluable will be included in the calculation of the DLT rate. Additional patients will be enrolled, if necessary, to ensure an adequate number of DLT-evaluable patients.

The primary estimand for Part B is the effect of BDTX-189, when administered at the RP2D, on objective response rate as assessed by BICR and per RECIST v1.1. It is described by the following attributes:

- Population: Patients with solid tumors containing mutations falling into one of the MTC-A through MTC-G groupings as reflected by the inclusion/exclusion criteria outlined in Sections 3.1 and 3.2.
- Variable: Objective responses defined as CR or PR as assessed by BICR and per RECIST v1.1, which occur from the date of first dose of study treatment until the date of the first documentation of PD, death or start of new anti-cancer therapy. Objective responses must be confirmed by repeat assessments performed at least 4 weeks later.

- Population-level summary: Objective response rate, defined as the proportion of patients in the analysis population with an objective response. Separate summaries will be estimated for various combinations of MTC groupings and tumor types.
- Intercurrent events: Estimation will be based on a “while on treatment” strategy. Patients who do not have a post-baseline tumor assessment or patients who receive subsequent anti-cancer therapies, have PD, die, or otherwise stop tumor assessments prior to experiencing a CR or PR will be considered non-responders.

9.3. Sample Size Considerations

9.3.1. Phase 1 (Part A)

The Phase 1 dose-escalation portion of the study will utilize a BOIN design as described in Section 4.3.1 and [Appendix G](#). Part A will enroll approximately 36 DLT-evaluable patients to the QD schedule, and approximately 24 additional DLT-evaluable patients may be treated in the dose-escalation portion to assess the BID schedule. The number of DLT-evaluable patients in Part A will not exceed 60, excluding patients in the accelerated titration step. Because both a QD and BID schedule are being evaluated and one RP2D and schedule will be selected, the Safety Expansion cohort(s) will include up to 48 patients, including a minimum of 12 patients for PK evaluation of a smaller and reformulated 200 mg tablet. In addition, up to 16 PK-evaluable patients will be enrolled to evaluate food-effect for a total of up to approximately 128 evaluable patients in Part A. The final sample size will depend on the dosing schedule, the number of DLTs, and the total number of cohorts treated before a DLT is observed and the MTD is determined.

9.3.2. Phase 2 (Part B)

For Cohorts 1, 2, and 5, the sample size was determined for each cohort independently. For Cohorts 3 and 4, the sample size was determined for each subgroup within a cohort independently.

The rationale for the different null hypotheses and target ORR values for each cohort/subgroup is discussed in Section 4.2.

Sample sizes for Cohorts 1-5 were estimated using nQuery version 8.6. The following sections provide the details of sample size considerations for each cohort and a summary of sample size for each cohort for various scenarios.

9.3.2.1. Sample Size Considerations for Cohorts 1 and 2

The sample size in each cohort will be based on a Simon 2-stage optimal design ([Simon 1989](#)), with the modification of adding an additional earlier assessment of futility. Therefore, Cohorts 1 and 2 will be evaluated in 3 stages.

Each cohort is designed to provide approximately 80% power to detect a true target ORR of 30%, while rejecting a null ORR of 17.5% at a nominal 1-sided alpha level of 0.05. For each cohort, 15 patients will initially be enrolled. If no patient has an objective response at the end of Stage 1, enrollment to the cohort will stop, otherwise an additional 16 patients will be enrolled. If 6 or fewer of the 31 total patients have objective responses at the end of Stage 2, enrollment to

the cohort will stop, otherwise an additional 54 patients will be enrolled. The null hypothesis will be rejected if at least 21 of the 85 total patients have objective responses.

A small number of first-line NSCLC patients may be enrolled to Cohort 1, in which case, these patients will be analyzed separately and will not count towards the numbers of patients described above.

[Table 12](#) provides the operating characteristics for Cohorts 1 and 2.

Table 12 Operating Characteristics for Cohorts 1 and 2

	Cumulative Probability of Stopping for Futility (Number of Responders/Total N) ¹			
	Stage 1 (0/15)	Stage 2 (≤ 6/31)	Stage 3 (≤ 20/85)	
True ORR = 17.5%	0.0558	0.7081	0.9541	Overall Type I Error: 0.0459
True ORR = 30%	0.0047	0.1355	0.1992	Overall Type II Error: 0.1992

¹ Based on exact binomial distribution.

9.3.2.2. Sample Size Consideration for Cohort 3

Cohort 3 will include 5 distinct mutational type subgroups (MTC-B, MTC-C, MTC-D, MTC-E and MTC-F) with each being evaluated independently.

The sample size in each subgroup will be based on a Simon 2-stage optimal design ([Simon 1989](#)). Each subgroup is designed to provide approximately 80% power to detect a true target ORR of 20%, while rejecting a null ORR of 5% at a nominal 1-sided alpha level of 0.05. For each subgroup, 10 patients will initially be enrolled. If no patient has an objective response at the end of Stage 1, enrollment to the subgroup will stop, otherwise an additional 19 patients will be enrolled. The null hypothesis will be rejected if at least 4 of the 29 total patients have objective responses.

[Table 13](#) provides the operating characteristics for each Cohort 3 subgroup.

Table 13 Operating Characteristics for Cohort 3

	Cumulative Probability of Stopping for Futility (Number of Responders/Total N) ¹		
	Stage 1 (0/10)	Stage 2 (≤3/29)	
True ORR = 5%	0.5987	0.9532	Overall Type I Error: 0.0468
True ORR = 20%	0.1074	0.1989	Overall Type II Error: 0.1989

¹ Based on exact binomial distribution.

9.3.2.3. Sample Size Considerations for Cohort 4

Cohort 4 will include patients from 3 distinct cancer-type subgroups (NSCLC, biliary or cervical cancer), with each being evaluated independently.

The sample size in each subgroup will be based on a Simon 2-stage optimal design ([Simon 1989](#)). Each subgroup is designed to provide approximately 80% power to detect a true target ORR of 20%, while rejecting a null ORR of 5% at a nominal 1-sided alpha level of 0.05. For each subgroup, 10 patients will initially be enrolled. If no patient has an objective response,

enrollment to the subgroup will stop, otherwise an additional 19 patients will be enrolled. The null hypothesis will be rejected if at least 4 of the 29 total patients have objective responses.

Table 14 provides the operating characteristics for each Cohort 4 subgroup.

Table 14 Operating Characteristics for Cohort 4

	Cumulative Probability of Stopping for Futility (Number of Responders/Total N) ¹		
	Stage 1 (0/10)	Stage 2 (≤3/29)	
True ORR = 5%	0.5987	0.9532	Overall Type I Error: 0.0468
True ORR = 20%	0.1074	0.1989	Overall Type II Error: 0.1989

¹ Based on exact binomial distribution.

9.3.2.4. Sample Size Considerations for Cohort 5

Cohort 5 will have a heterogeneous patient population with many cancer types and MTC subsets. This cohort will include all eligible patients who cannot be assigned to Cohorts 1-4.

The sample size will be based on a Simon 2-stage optimal design (Simon 1989). The cohort is designed to provide approximately 80% power to detect a true target ORR of 20%, while rejecting a null ORR of 10% at a nominal 1-sided alpha level of 0.05. Thirty patients will initially be enrolled. If 3 or fewer patients have an objective response, enrollment to the cohort will stop, otherwise an additional 59 patients will be enrolled. The null hypothesis will be rejected if at least 14 of the 89 total patients have objective responses.

Table 15 provides the operating characteristics for Cohort 5.

Table 15 Operating Characteristics for Cohort 5

	Cumulative Probability of Stopping for Futility (Number of Responders/Total N) ¹		
	Stage 1 (≤3/30)	Stage 2 (≤13/89)	
True ORR = 10%	0.6474	0.9522	Overall Type I Error: 0.0478
True ORR = 20%	0.1227	0.1982	Overall Type II Error: 0.1982

¹ Based on exact binomial distribution.

9.4. Analysis Population

The following analysis populations will be used:

- The Intent-To-Treat (ITT) population is defined as all patients who signed informed consent. The ITT population is the primary population for the summarization of enrollment.
- The Full Analysis (FA) population is defined as all patients who receive at least one dose of BDTX-189. The FA population is the primary population for both safety and Part A efficacy analyses.
- The Per-Protocol Efficacy (PPE) population is defined as all FA population patients who meet the eligibility criteria, receive BDTX-189, and have at least one baseline and post-baseline response assessment. The PPE population will be used for exploratory sensitivity analyses.

- The DLT-evaluable population will consist of all patients in Part A (excluding those patients in the Food-Effect Cohort) who receive at least 75% of the planned oral doses during Cycle 1 and complete all required safety evaluations or who have a DLT in Cycle 1.
- The Pharmacokinetic (PK) population is defined as all patients who receive at least one dose of BDTX-189 and have at least one post-dose PK blood collection with associated bioanalytical results.
- The Pharmacodynamic (PDx) population is defined as all patients who receive at least one dose of BDTX-189 and have post-baseline ctDNA samples or have paired on-treatment tumor tissue biopsy results.

9.5. Data Analysis

Descriptive statistics, including mean, median, standard deviations, and range for all continuous measures will be tabulated and reported. Percentages and frequencies for all categorical measures will also be presented. Time to event endpoints will be reported using Kaplan-Meier estimates, with approximate 2-sided 95% confidence intervals (CIs) for median time to event.

9.5.1. Demographics and Baseline Characteristics

Demographic and baseline disease characteristics will be summarized descriptively. Data to be tabulated will include demographic features such as age, sex, and race, as well as disease-specific characteristics.

The number and percentages of patients who were screened, registered, and treated; who completed the treatment/study; and who were withdrawn from treatment/study for any reasons will be presented overall and by treatment cohort for Part A and Part B.

9.5.2. Hypotheses to be Tested

Part B Cohorts 1 and 2 of the study are designed to test the null hypothesis that the true ORR of BDTX-189 is less than or equal to 17.5%, while having sufficient power to detect (i.e., reject the null hypothesis with) a true ORR of 30%.

Part B Cohorts 3-4 of the study are designed to test the null hypothesis that the true ORR of BDTX-189 is less than or equal to 5%, while having sufficient power to detect a true ORR of 20%.

Part B Cohort 5 of the study is designed to test the null hypothesis that the true ORR of BDTX-189 is less than or equal to 10%, while having sufficient power to detect a true ORR of 20%.

9.5.3. Efficacy Analysis

The Investigator-assessed objective response is a secondary endpoint for Part A. BICR-assessed objective response is a primary endpoint for Part B. Secondary objectives of Part B include evaluating the Investigator-assessed objective response, and evaluating both the Investigator and BICR-assessed duration of response (DOR), disease control rate (DCR), and PFS as evidence of the antitumor activity of BDTX-189. Evidence of antitumor activity for ORR, DOR, DCR, and PFS will be determined by RECIST v1.1. OS is also a secondary endpoint for Part B.

- Objective Response Rate (ORR), defined as the proportion of patients with a best overall response of CR or PR recorded from baseline until PD, start of subsequent anti-cancer therapy, or death due to any cause according to the RECIST Version 1.1 criteria (see [Appendix B](#)). The Part B primary endpoint will be based on the confirmed ORR (i.e., 2 CRs or PRs at least 4 weeks apart). Unconfirmed best overall response and response rates will also be summarized.
- Duration of Response (DOR), defined as the time between first documentation of a response (CR or PR) and first evidence of PD according to RECIST v1.1 or death due to any cause. In case a patient does not have progression or death, DOR is censored at the date of last adequate tumor assessment (defined as an assessment of CR, PR, or SD). Duration of response analysis will include only the responders.
- Disease Control Rate (DCR) is defined as the proportion of patients with a best overall response of CR, PR, or SD.
- Progression-Free Survival (PFS), defined as the time from the first day of study drug administration to PD as defined by the RECIST Version 1.1 criteria, or death. Patients who are alive and free from PD will be censored at the date of last adequate tumor assessment.
- Overall Survival (OS), defined as the time from the first day of study drug administration to death. Patients who are alive will be censored at the last date the patient was known to be alive.

For ORR and DCR, patients without an adequate post-baseline tumor assessment will be classified as NE and considered non-responders. ORR estimates and the associated 95% CIs (based on exact binomial distributions) in each cohort/subgroup will be calculated.

For PFS and OS, Kaplan-Meier curves will be generated, and the median time-to-event and the associated 2-sided 95% CIs will be provided.

Efficacy analyses in Part A will be performed using the FA Population by cohort and combined. Part B efficacy summaries will be performed by cohort/subgroup.

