^u Archival tissue sample is required for patients in the Safety Expansion who have allosteric *ErbB* mutations and archival tissue available; tissue block is preferred. In the event that a tissue block is unavailable, 12-20 formalin-fixed paraffin-embedded unstained slides may be submitted. If there is not enough archival tumor tissue, a new tumor tissue biopsy sample must be obtained during screening, prior to starting study treatment. (See Section [5.7.1](#))

^v May be performed any time within 28 days prior to C1D1 and includes assessments completed at the clinical site as part of standard of care, and prior to the signing of the informed consent, if the assessments were performed in compliance with the protocol requirements. Baseline assessment must include CT or MRI imaging of the chest and abdomen, through the level of the adrenals, and brain, if clinically indicated, as well as other sites of known disease.

^w A smaller and reformulated 200 mg tablet may be introduced and supplied to some patients during the Safety Expansion of Part A; these tablets will be available to all patients enrolling onto Part B. Patients in Part A who initiated treatment with the larger-200 mg tablet may be switched to the smaller and reformulated 200 mg tablet at the beginning of their subsequent cycles. Detailed PK sampling will be collected on Day 15 (i.e., after 14 days of daily treatment with the smaller 200 mg tablet) of that subsequent cycle according to [Table 8](#).

^x From the 30-Day Safety Follow-up visit, follow-up for OS, PFS, and first subsequent anti-cancer therapy, if available, will be obtained every 3 months (\pm 14 days) until 2 years after the patient's first dose of study drug, death, loss to follow-up, withdrawal of consent, or end of the whole trial. Follow-up information about overall survival may be obtained by phone.

Table 3 BDTX-189-01 Schedule of Assessments Part B

Flow Chart (Part B) Study period	Screening	Part B BDTX-189 Treatment Period									
Study Procedures ^a		Cycle 1			Cycle 2 (±2 days)		Cycle 3, 4, 5 and every other cycle thereafter (±2 days)	End of Treatment ^c	30-Day Safety Follow-up Visit ^d	Unscheduled Visits ^e	PFS/OS ^u
Study Day	≤28 days prior to C1D1	1 ^b	8	15	1	8	15	1	Within 3 days of decision to discontinue study drug	30 days after last dose (±3)	
Informed consent	X ^f										
Inclusion / exclusion criteria	X										
Medical and disease history	X										
Demographics	X										

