- ^s Tumor assessment (CT or MRI of chest, abdomen, and pelvis, plus other sites of known disease at baseline) will be performed every 6 weeks for the first 8 cycles, and then every 12 weeks thereafter. Imaging should be completed within a window of -3 days prior to D1 of odd cycles and should be reviewed before study drug administration on D1 for dosing determination. Patients who discontinue treatment for reasons other than PD will undergo tumor assessment in accordance with the original schedule relative to C1D1. Tumor assessment/imaging must be performed at the time of treatment discontinuation, unless it has been done within the past 4 weeks. If disease progression according to RECIST (version 1.1) is documented at any time, no further tumor/response assessment will be required.
- ^t May be performed any time within 28 days prior to C1D1 and includes assessments completed at the clinical site as part of standard of care, and prior to the signing of the informed consent, if the assessments were performed in compliance with the protocol requirements. Baseline assessment must include CT or MRI imaging of the chest and abdomen, through the level of the adrenals, and brain, if clinically indicated, as well as other sites of known disease.
- ^u From the 30-Day Safety Follow-up visit, follow-up for OS, PFS, and first subsequent anti-cancer therapy, if available, will be obtained every 3 months (\pm 14 days) until 2 years after the first dose of study drug, death, loss to follow-up, withdrawal of consent, or end of the whole trial. Follow-up information about overall survival may be obtained by phone.
- ^v Archival tissue sample is mandatory for patients in Part B who have archival tissue available; a tissue block is preferred. In the event that a tissue block is unavailable, 12-20 formalin-fixed paraffin-embedded unstained slides may be submitted. If there is not enough archival tumor tissue, a new tumor tissue biopsy sample must be obtained during screening, prior to starting study treatment. (See Section [5.7.1](#)).

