5.4.3. Extended Follow-up Period (Safety Expansion and Part B)

For patients participating in Safety Expansion portion of Part A and all patients in Part B, additional follow-up for OS, PFS, and the first subsequent anti-cancer therapy after the 30-Day Safety Follow-up visit will be performed every 3 months (± 14 days) until 2 years after the first study drug dose if the patient has stopped treatment prior to PD based on RECIST Version 1.1 as assessed by the Investigator (see [Appendix B](#)) or another withdrawal criterion is met:

- Start of a new anti-cancer therapy.
- Lost to follow-up.
- Death.
- End of the whole study.

Follow-up information for OS may be obtained by phone.

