9.6. Analysis Time Points

9.6.1. Final Analysis

The final analysis for a given cohort in Part B will occur once all patients in the cohort are enrolled and have either been treated for at least 6 months or discontinued treatment for any reason prior to 6 months after their first dose of study drug.

The final analysis of the entire study will occur after all patients have discontinued the study (Part A will be separate from Part B).

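### Survival contacts end 2 years after first dose only for patients off BDTX-189, so the OS curve beyond month 24 rests almost wholly on patients still on drug; Section 5.4.3 also conflicts with the schedule footnotes

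*Combined protocol and SAP*

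**What the plan says.** OS runs from first dose to death (Section 9.5.3). The censoring rule is "Patients who are alive will be censored at the last date the patient was known to be alive". The planned output is: "For PFS and OS, Kaplan-Meier curves will be generated, and the median time-to-event and the associated 2-sided 95% CIs will be provided". Its status is stated as "OS is also a secondary endpoint for Part B"; Table 4 also lists OS for the Safety Expansion.

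Two schedule footnotes set the off-treatment survival contacts. They start at the 30-Day Safety Follow-up visit and recur every 3 months. For Part B (Table 3 footnote u) they run "until 2 years after the first dose of study drug, death, loss to follow-up, withdrawal of consent, or end of the whole trial". For the Safety Expansion (Table 2 footnote x) they run "until 2 years after the patient's first dose of study drug, death, loss to follow-up, withdrawal of consent, or end of the whole trial".

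Section 5.4.3 covers the same follow-up with a narrower rule: "until 2 years after the first study drug dose if the patient has stopped treatment prior to PD based on RECIST Version 1.1". It then lists the start of a new anti-cancer therapy among the criteria that end follow-up.

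Treatment has no fixed length. The Synopsis ends it at progression or unacceptable toxicity, and Sections 3.3, 4.4 and 5.3.3 allow it to continue past progression. Adverse events are collected to 30 days after the last dose (Section 3.3). After that, Section 8.1.5 asks only for drug-related SAEs and deaths judged treatment-related. On timing, Section 9.6.1 says: "The final analysis of the entire study will occur after all patients have discontinued the study".

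**The concern.** Kaplan-Meier needs censored patients to have the same outlook as those still at risk. Here the end of observation depends on treatment status:

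- A patient alive and off drug at month 24 leaves the risk set at about that time.
- A patient still on drug stays in it.
- A patient who stops drug after month 24 is followed for about 30 more days, because the 2-year limit has already passed.

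Stopping is driven mainly by progression and toxicity, so it probably predicts death. If so, the curve flattens after month 24 because of the follow-up rule rather than because of survival. In a single-arm study the OS curve will be set beside external data, and this error would favour the drug.

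**Working it through.** **No plan figure to reproduce.** The documents give no OS event count, power or assumed survival rate, so the check is a model of the follow-up rule.

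**Inputs.**
- Median time on treatment of 4.2, 7.3 or 14.0 months, using median PFS values cited in Section 1.1.3 as stand-ins.
- Median survival after stopping of 8, 12 or 18 months (assumed; not in the documents).
- Death hazard on treatment of 0.005 or 0.02 per month (assumed; not in the documents).
- Exponential times. Observation ends at the later of month 24 and last dose plus 1 month, with a data cut no earlier than 36 months.

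**One scenario in closed form** (7.3 months, 12 months, 0.005). Let a = ln 2/7.3 = 0.0950 be the monthly rate of stopping, b = ln 2/12 = 0.0578 the death hazard off drug, and c = 0.005 the death hazard on drug.

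- Alive on drug: On(t) = exp[−(a+c)t].
- Alive off drug: Off(t) = a/(a+c−b) × {exp(−bt) − exp[−(a+c)t]}, where a/(a+c−b) = 2.251.
- Month 24: On = 0.091 and Off = 2.251 × (0.250 − 0.091) = 0.358. True OS is 0.449, and 0.358/0.449 = 80% of survivors are off drug.
- Month 36: On = 0.027 and Off = 2.251 × (0.125 − 0.027) = 0.220. True OS is 0.247.
- After month 24, each on-drug patient in the risk set is accompanied by m = 2.251 × [exp(a+c−b) − 1] = 0.097 patients who stopped within the past month.
- The risk-set hazard is (c + m·b)/(1 + m) = (0.005 + 0.097 × 0.0578)/1.097 = 0.0097 per month.
- Kaplan-Meier at month 36 is 0.449 × exp(−0.0097 × 12) = 0.400, against a true 0.247.

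Simulation with 400,000 patients gives 0.400 against 0.246.

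**All 18 combinations.**
- Up to month 24, Kaplan-Meier equals the truth.
- At month 24, 45% to 97% of survivors are off drug.
- The excess is about 3 to 9 points at 30 months and 5 to 16 points at 36 months.
- The median is correct in the 14 combinations where it is below 24 months. It is too high in the other 4; for example, a true 27.6 months is estimated as about 39, and a true 25.3 as about 26.

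**Two controls.** With equal death hazards on and off drug, the bias disappears (0.125 against 0.125 at 36 months). With contacts continued for everyone (7.3 months, 12 months, 0.01), the curve is correct (0.228 against 0.228).

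**How many patients this concerns.** In the worked scenario, 0.027 × 1.097 = 0.030 of a cohort is at risk at month 36 if everyone could be followed that long: 2.6 of 85, or 0.9 of 29. If the data cut falls evenly between 24 and 42 months after first dose (assumed), one third reach month 36, leaving 0.9 of 85 or 0.3 of 29. Across the 18 combinations with that cut, the expected number of 85 at risk is 0.3 to 11.6 at month 30 and below 0.1 to 4.2 at month 36.

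**If Section 5.4.3 governed OS.** Suppose contacts end at new therapy, on average 2 months after stopping, with 12 months' median survival after stopping and an on-drug hazard of 0.01 (all assumed). Then 12-month OS is estimated as 0.76 against a true 0.65 with 4.2 months on treatment, and 0.81 against 0.72 with 7.3 months. This bias lies well inside the first 24 months.

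**The case against.** The strongest reply is that little of this would reach a reported number. Section 9.5.3 plans a curve and a median, with no landmark rate beyond 24 months. Most patients are pretreated and the cited median PFS values are 4.2 to 14.0 months, so a median OS above 24 months is not the obvious expectation. Follow-up is also short. Preliminary clinical data existed by Amendment 2 (July 2020) and Part B had not opened at Amendment 3 (June 2021). If the study lasts the planned 48 months or so, the first Part B patient has at most about 37 months. Cohorts and subgroups of 29 to 89 would then have few patients at risk in the affected range. The cohort analyses come earlier still, about 6 months after the last patient's first dose, and all hypothesis tests use ORR. Section 9.1 also leaves further detail to the SAP. All of this stands, and it limits the size of the problem. It does not make the tail of the planned curve valid, and nothing in the text supplied cuts the curve at 24 months.

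A reader might infer that OS is overstated in every cohort. The documents do not support that: the direction needs a lower death hazard on drug than off it, no hazards are given, and Dose Escalation has no extended OS follow-up. A reader might also infer that only progression-free patients remain at risk after month 24. That is not right either, because treatment past progression is allowed and progression-free patients who have stopped drug are censored.

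A cap at 24 months does discard real survival time. Continuing survival calls for all patients to death or study end is a sound alternative, and telephone contact is already permitted.

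**Conclusion.** The point holds in limited form. In Part B and the Safety Expansion, censoring of OS after month 24 depends on treatment status. If patients on drug have the lower death hazard, the tail of the curve and any median above 24 months are biased upward. The percentage-point figures are illustrative and describe a part of the curve that would hold few patients per cohort. Under the footnote rule, everything up to month 24 is sound.

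The conflict between Section 5.4.3 and the two footnotes matters at least as much. Section 5.4.3 ties follow-up to stopping before progression and ends it at new therapy. Read as governing OS, it makes censoring informative from early on, and a 24-month cap alone would not cure that. The cap works only once these passages agree. This is a secondary-endpoint matter that is worth fixing because the remedy is cheap.

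**What to change.** 1. Reconcile Section 5.4.3 with Table 2 footnote x and Table 3 footnote u. State that survival status is collected for every treated patient in Part B and the Safety Expansion to 24 months after first dose, regardless of progression or new anti-cancer therapy.
2. Add to Section 9.5.3 and the SAP: OS for all patients in Part B and the Safety Expansion is administratively censored at 24 months after first dose; Kaplan-Meier estimates are reported to 24 months only; a median beyond that is given as not reached; patients known to be alive later are listed.

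The cost is a few sentences. Contacts increase only where sites have been following the narrower Section 5.4.3 rule. The downside is that survival beyond 24 months is listed, not estimated.
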